7.1.4 Conventions for Missing Adverse Event Dates

Missing AE dates will not be imputed. In the event an AE is missing onset date information a consistent and reasonable effort will be made to associate the event to one of the 4 regimens in the study. A few illustrative examples follow:

- Onset date is missing and event stop date predates Day 1 then the event will be evaluated as pre-treatment.
- Onset date is missing and event stop date is within Period X, then AE will be associated with the regimen for Period X.
- Onset date is partial, day missing month available. Then the event will be associated to the Regimen given in earliest Period compatible for the month of onset.

7.1.5 Conventions for Missing Concomitant Medication Dates

Missing dates for concomitant medication will not be imputed. However, if necessary, similar strategies as described in section 7.1.4 will be used to associate the concomitant medication to the trial periods/regimens.

7.2 Analysis Sets

The **safety set** will include all randomized subjects who receive at least 1 dose of study medication, including subjects who do not complete the study. Subjects in this set will be used for demographic and baseline characteristics as well as safety summaries.

The **PK set** will consist of all subjects in the safety set who have sufficient plasma concentration data to facilitate the derivation of at least 1 PK parameter. Details regarding how to handle missing data will be predefined in the Clinical Pharmacology Analysis Plan.

7.3 Disposition of Subjects

Study Information, including date of first subject signing Informed Consent Form (ICF), date of first/last study drug, date of last subject's last visit/contact, date of last subject's last procedure for collection of data for primary endpoint, Medical Dictionary for Drug Regulatory Activities (MedDRA) Version, World Health Organization Drug Dictionary (WHODrug) Version, and SAS Version used for creating the datasets, will be summarized.

The eligibility of subjects will be summarized, along with the primary reasons of screen failure as recorded in eCRF.

Number of subjects randomized will be tabulated by treatment sequence and overall.

Disposition of all enrolled subjects will be tabulated. Categories will include:

- Subjects who were randomized but not treated
- Subjects who completed the study

- Subjects who prematurely discontinued study

Primary reasons for discontinuing study, as entered on the eCRF will be tabulated.

7.4 Demographic and Other Baseline Characteristics

Demographic and study baseline characteristics, including age at first dose administration, sex, ethnicity, race, height (cm), weight (kg), and body mass index (kg/m^2), will be summarized by sequence and overall. Demographic and baseline characteristics variables will not be analyzed inferentially. Demographic variables for subjects screen but not randomized, i.e. screen failure, will be summarize similarly.

7.5 Medical History and Concurrent Medical Conditions

Medical history, defined as significant conditions or diseases that resolved at or prior to the time of informed consent, and concurrent medical conditions, defined as significant conditions or diseases that are present at signing of informed consent, will be coded using the MedDRA coding system. Medical history and concurrent medical conditions will be listed by subject number. There will be no summary or inferential analysis of medical history and concurrent medical conditions.

7.6 Medication History and Concomitant Medications

Medication history information includes any medication relevant to eligibility criteria stopped at or within 28 days prior to signing of informed consent. Concomitant medication is any drug given in addition to the study drug, taken at any time from signing of informed consent through the end of study. Medication history and concomitant medications will be coded using the WHODrug. Listings for medication history and concomitant medications will be produced by subject number. There will be no summary or inferential analysis of medication history and concomitant medications.

7.7 Study Drug Exposure and Compliance

All doses of study medication will be administered during confinement. Dosing data, including dosing time will be provided by subject and visit in the listings. Data on eCRFs for meals received will also be provide in the data listings.

7.8 Efficacy Analysis

Not applicable.

7.9 Pharmacokinetic/Pharmacodynamic Analysis

7.9.1 Pharmacokinetic Analysis

The schedule for blood samples for PK analysis of alogliptin and pioglitazone is listed in Table 1.

The concentration of both alogliptin and pioglitazone in plasma will be summarized by regimen over each scheduled sampling time point using descriptive statistics (arithmetic mean, SD, CV%, median, minimum and maximum). Individual plasma concentration data versus time will be listed. In addition, the figures for mean plasma concentrations of alogliptin (pioglitazone) versus time (linear and semi-log scale) will be generated.

PK parameters for alogliptin and pioglitazone will be estimated using non-compartmental methods. Additional details concerning the calculation and reporting of PK parameters can be found in the Clinical Pharmacology Analysis Plan (CPAP) .

Descriptive statistics (N, mean, SD, CV%, median, minimum and maximum) will be used to summarize the PK parameters for alogliptin and pioglitazone by regimen. In addition, geometric means will be computed for AUCs and C_{max} . The PK parameters of interest are listed in Table 2.

Box plots for both alogliptin and pioglitazone C_{max} and AUC_{72} will be generated by regimen and will be presented Regimen A versus Regimen B and Regimen C versus Regimen D.

Table 1 Collection of blood samples for PK analysis

| Analyte | Matrix | Dosing Day | Scheduled Time (hours) |
|--------------|--------|------------|---|
| Alogliptin | Plasma | 1 | Predose (within 15 minutes prior to dose) and 0.25, 0.5, 1, 1.5, 2, 3, 4, 6, 8, 12, 16, 24, 36, 48, and 72 hours postdose |
| Pioglitazone | Plasma | 1 | Predose (within 15 minutes prior to dose) and 0.25, 0.5, 1, 1.5, 2, 3, 4, 6, 8, 12, 16, 24, 36, 48, and 72 hours postdose |

Table 2 Pharmacokinetic Parameters

| Symbol/Term | Definition |
|-------------|---|
| AUC_{72} | Area under the concentration-time curve from the time 0 to time 72 hours. |
| AUC_t | Area under the concentration-time curve from time 0 to time t. |
| CCI | |
| C_{max} | Maximum observed concentration |

| | |
|-------------|--|
| CL/F | Apparent clearance after extravascular administration, calculated using the observed value of the last quantifiable concentration. |
| λ_z | Terminal disposition phase rate constant |
| $t_{1/2z}$ | Terminal disposition phase half-life |
| t_{max} | Time of first occurrence of C_{max} |

For each analyte, an analysis of variance (ANOVA) will be performed on natural logarithm transformed C_{max} and AUC_{72} with factors for sequence, the subject nested within sequence, period and regimen. The random effect subject nested within sequence will be the error term for testing the sequence effect. Other factors will be tested with the residual as the error term. For the relative bioavailability (BA) determination, pairwise comparisons will be performed to assess the relative BA of alogliptin and pioglitazone via point estimates and 90% confidence interval (CI) for the ratio of C_{max} and AUC_{72} central values for Regimen A (test) versus Regimen B (reference) as well as Regimen C (test) versus Regimen D (reference). CCI [REDACTED]

A conclusion of bioequivalence in the PK of each analyte between test regimen will be reached if the 90% CIs for C_{max} and AUC_{72} are within the (0.80-1.25) interval.

7.9.2 Pharmacodynamic Analysis

Not applicable.

7.10 Other Outcomes

Not applicable.

7.11 Safety Analysis

All summaries and analyses of safety data are based on subjects in the Safety Analysis Set. Unless otherwise specified, the safety data will be summarized by study arm.

7.11.1 Adverse Events

A treatment-emergent adverse event (TEAE) is defined as an adverse event (AE) or serious adverse event (SAE) that started or worsened after first study drug administration and within 14 days (30 days if SAE) of last dose of study drug (onset date – date of last dose + 1 ≤ 14), see Protocol Section 10.2.1.1. A TEAE will be attributed to a regimen if the TEAE occurs after administration of the study drug in a period and up to just prior to study drug administration in the next period. A TEAE that occurs after administration of the study drug in the last period and up to 14 days after the last study drug dose is attributed to the regimen received in the last period. All AE verbatim terms will be coded by system organ class (SOC) and preferred term using (PT) the MedDRA coding system. Any subject that doesn't not complete all 4 regimens/periods will be included in the AE summaries, and will be included in each of the regimens for which they

were treated and any AEs happening after their last regimen exposure (inclusive of 30 days) will be included in the tally of that regimen.

TEAEs will be summarized by regimen and overall. The tables will include the number and percentage (N [%]) of subjects reporting any event for that term. The denominator, within a regimen summary, will be the total number of subjects that received the regimen.

The following TEAE tables will be summarized by part.

- Overview of TEAEs.
- TEAEs by SOC and PT.
- Most Frequent TEAEs by PT term
- Most Frequent Non-Serious TEAEs by PT
- Relationship of TEAEs to Study Drug by SOC and PT.
- Study Drug-Related TEAEs by SOC and PT.
- Severity of TEAEs by SOC and PT.
- Severity of Drug-Related TEAEs by SOC and PT.

In addition, pretreatment events (PTEs) will be summarized overall by SOC and PT.

For each regimen and overall, subjects reporting more than one occurrence for a term (SOC or PT) being summarized will be counted only once using the most extreme incident (most severe for the severity tables and related for the relationship to study drug tables).

Most frequent TEAEs are those events occurred in at least $\geq 5\%$ (before any rounding) of subjects in a regimen.

Data listings will be provided for all TEAEs, PTEs, TEAEs that led to study discontinuation, TEAEs that led to abnormal liver functions, SAEs, AEs that resulted in death, and AEs occurring more than 30 days after the last dose of study medication.

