10.2 Procedures

10.2.1 Collection and Reporting of AEs

10.2.1.1 AE Collection Period

Collection of AEs will commence from the time the subject signs the informed consent to participate in the study and continue until 14±2 days after Study Exit Visit or the last dose of study medication.

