13.1.4 Subject Condition Assessments

Subject condition assessments will be performed using the Safety Set. All subject condition assessments, including AEs, clinical laboratory evaluations, 12-lead ECG results, and vital signs will be summarized with descriptive statistics, where appropriate, and presented in the data listings.

All AEs will be coded using MedDRA and presented in the data listings.

A postdose AE is defined as an AE that occurs after the subject receives the first dose of study medication and within 30 days after the last dose of study medication is received. Summary of AEs will include numbers and percentages of subjects experiencing AEs by system organ class and preferred term. AEs will also be summarized based on their intensity and relationship to study medication by system organ class and preferred term. If a subject has more than 1 AE that codes to the same preferred term, the subject will be counted only once for that preferred term within regimen. Similarly, if a subject has more than 1 AE within a system organ class category, the subject will be counted only once in the system organ class category within the regimen. In the intensity summary, a subject will be counted only in the highest intensity category for each preferred term and each organ class. In the relationship to study medication summary, a subject will be counted only in the highest relationship category for each preferred term and each system organ class. Each summary table will include incidences of adverse events for each regimen and overall.

All AE summary tables will be listed in the SAP.

AEs will be summarized using preferred term and primary system organ class.

Individual results for clinical hematology and serum chemistry laboratory tests that are outside of normal range and results that meet Takeda predefined criteria for markedly abnormal values will be considered as clinically significant and identified in summary tables, if applicable. Observed values and change from Baseline will be summarized by regimen. All laboratory values will be presented in the data listings.

Individual vital sign values that meet the Takeda predefined markedly abnormal criteria will be considered as clinically significant and identified in a summary table. The vital sign measurements at predefined time points and change from Baseline will be summarized by regimen. All vital signs data will be presented in the data listing.

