Appendix A Study Procedures

| Study Day: | Days -28 to -2 (b) | Drug Intake Periods 1 through 4 (a) | | | | | Study Exit (Day 4 of Period 4)/ Early Termination Visit | Follow-up Phone Call (d) |
|---|--------------------------|-------------------------------------|--------------|-------|-------|---------------------------------------|--|--------------------------------|
| | | Day -1 (Check- in) | Day 1 (c) | Day 2 | Day 3 | Day 4 (Period s 1, 2, and 3) | | |
| Informed consent | X | | | | | | | |
| Inclusion/exclusion criteria | X | X | | | | | | |
| Demographics and medical history | X | | | | | | | |
| Medication history | X | | | | | | | |
| Physical examination | X | X | | | | | X | |
| Vital signs (e) | X | X | X | | | X | X | |
| Height, weight and BMI | X | | | | | | | |
| Concomitant medications | X | X | X | X | X | X | X | X |
| 12-lead ECG (f) | X | X | | | | | X | |
| Clinical laboratory evaluations (g) | X | | X (h) | | | | X | |
| Urine drug, cotinine, and alcohol breath screen | X | X | | | X | X | X | |
| Urine pregnancy test (hCG) (i) | X | X | | | | | X | |
| HBsAg, Anti-HCV, HIV, and syphilis (i) | X | | | | | | | |
| Confinement | | X | X (j) | X (j) | | | | |
| Study drug dosing (k) | | | X | | | | | |
| PK blood collection (l) | | | X | X | X | X | X | |
| Predose/AE assessment (m) | X | X | X | X | X | X | X | X |

(a) There will be at least 7 days between the dose in 1 period and the dose in a subsequent period.

- (b) Screening may consist of 1 or more visits. Subjects will sign an informed consent form at the first visit and return to the clinic in a fasted state for safety laboratory testing at the second visit. Screening procedures must be performed within 28 days prior to administration of investigational product.
- (c) Day 1 of each drug intake period.
- (d) Follow-up phone call will be made 14 ± 2 days after study exit to inquire about any AE or SAEs, and concomitant medications taken since final dose. Any AE/SAE spontaneously reported within 30 days postdose will be included within the database as AEs.
- (e) Vital signs: oral body temperature, sitting blood pressure (after resting 5 minutes), respiratory rate, and pulse (beats per minute). Vital signs will be measured just prior to dosing on Day 1 of periods 1 through 4. When vital signs are scheduled at the same time as blood draws, the blood draw will take priority and vital signs will be obtained within 0.5 hour before or after the scheduled blood draw.

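### SAP 7.11.1 stops counting non-serious TEAEs about 14 days after the last dose, although Protocol 13.1.4 counts all AEs to 30 days and other parts of SAP 7.11.1 use 30

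*SAP*

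**What the plan says.** **Protocol.** Section 13.1.4 defines a postdose AE as one that occurs after the first dose and "within 30 days after the last dose of study medication is received", without distinguishing serious from non-serious events. Section 10.2.1.1 governs collection rather than analysis, and runs AE collection until "14±2 days after Study Exit Visit or the last dose of study medication".

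**SAP.** Section 5.2 keeps the percentage of subjects with a postdose AE as an additional endpoint but does not define the term. The working definition is the TEAE in 7.11.1, which contains these rules:

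- The window is "within 14 days (30 days if SAE) of last dose of study drug", with a formula requiring onset date minus last-dose date plus 1 to be at most 14. The stated basis is "see Protocol Section 10.2.1.1".
- A TEAE after the final period's dose and "up to 14 days after the last study drug dose is attributed to the regimen received in the last period".
- For subjects who do not complete all four periods, "any AEs happening after their last regimen exposure (inclusive of 30 days) will be included in the tally of that regimen".
- The last item in the data listings is "AEs occurring more than 30 days after the last dose of study medication".

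Note (d) of SAP Appendix A adds: "Any AE/SAE spontaneously reported within 30 days postdose will be included within the database as AEs". SAP 7.13, on changes to the plan, is marked as not applicable.

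**The concern.** The SAP replaces a 30-day analysis definition with a 14-day one for non-serious events and does not say so. The section it cites sets how long AEs are collected. It does not set which events are analysed.

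The rules in 7.11.1 also disagree with one another. Taken literally, a non-serious AE 20 days after the last dose is tallied for a non-completer and left out for a completer. Two programmers could follow 7.11.1 in good faith and produce different AE tables, and neither need match the protocol. Comparing AE data between the combination tablet and the separate tablets is the study's only additional objective, so the definition should be unambiguous.

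**Working it through.** Let d = onset date − last-dose date, in days. All inputs are the rules set out above, with doses 7 days apart (Protocol 6.1). The plan states no day count of its own to reproduce.

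**1. Onset days not counted for a completer's non-serious AE**

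| Reading | SAP limit | Protocol limit | Uncounted d | Days |
|---|---|---|---|---|
| Prose in both | 14 | 30 | 15–30 | 16 |
| +1 applied to both | 13 | 29 | 14–29 | 16 |
| SAP formula against plain 30 days | 13 | 30 | 14–30 | 17 |

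**2. Where such an event goes.** The listings named in 7.11.1 cover TEAEs (all of them, plus two subsets), pretreatment events, SAEs, fatal AEs and AEs with d > 30. By the prose, a completer's non-serious, non-fatal AE with d = 15–30 belongs to none of these. Note (d) of Appendix A nevertheless puts it in the database if it is spontaneously reported.

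**3. Counted window from first dose, literal reading.** Doses fall at offsets 0, 7, 14 and 21.

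- Completer under the SAP: 21 + 14 + 1 = 36 days (21 + 13 + 1 = 35 by the formula).
- Completer under Protocol 13.1.4: 21 + 30 + 1 = 52 days (51 with +1).
- Non-completer stopping after Period k: 7(k − 1) + 31 = 31, 38 or 45 days for k = 1, 2, 3 (30, 37 or 44 with +1).

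Stopping after Period 2 or 3 therefore gives a longer counted window than completing.

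**4. How much of the gap is actively solicited.** The follow-up call is timed from the last dose in Protocol 6.1 and 9.3.5, and from study exit in note (d) of Appendix A. Study exit is Day 4 of Period 4, so d = 3.

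| Call anchor | Call at d | Solicited but uncounted, prose | Same, formula | Left to spontaneous reports |
|---|---|---|---|---|
| Last dose | 12–16 | 0–2 days | 0–3 days | 14–16 (14–17 by formula) |
| Study exit | 15–19 | 1–5 days | 2–6 days | 11–15 (both) |

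Solicited days are max(0, call day − 14) by the prose and max(0, call day − 13) by the formula. The remainder is taken from 16 or 17 respectively. With the study-exit anchor, every scheduled call falls after the SAP cut-off.

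**5. Regimen attribution.** The formula has no SAE branch, and the last-period sentence stops at 14 days. The regimen for a completer's SAE on days 15–30 is therefore not clearly assigned, although the preceding general attribution sentence could be read to cover it.

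**The case against.** The strongest reply has five parts.

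- **The 14 days has a source.** Protocol 10.2.1.1 and note (m) of Appendix A end routine collection around the follow-up call, and Protocol 13.1 leaves further detail on analysis variables to the SAP. The tension between 14 and 30 days starts in the protocol. This explains the choice, but 13.1.4 remains the definition of the analysed event and the SAP does not declare that it departs from it.
- **The non-completer sentence may only assign a regimen**, with 30 days as the outer limit for SAEs, since the post-dose summary tables are all TEAE tables. That reading is possible, so the completer/non-completer difference is a consequence of the literal wording, not a certainty. The comparison in step 3 depends on the literal reading. It also concerns the overall column, because regimen columns use their own denominators. At the planned 14% drop-out, about 10 of 72 subjects would be involved. Those who withdrew consent have no call entry in the eCRF (Protocol 9.3.5), which narrows the difference further.
- **No event disappears.** Protocol 13.1.4 and SAP 7.1 both promise complete listings. This is correct, but a listing does not restore an event to the TEAE tables or to the endpoint percentage.
- **The +1 follows the day numbering in SAP 7.1.2.** It does, and the mismatch is one day. It still disagrees with the last-period sentence, which runs to 14 days after the dose.
- **The call anchor is a separate matter.** Agreed. It affects how many gap days are solicited, not whether the gap exists.

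**Conclusion.** The concern holds and is minor. Followed as written, SAP 7.11.1 gives a postdose-AE percentage that departs from Protocol 13.1.4 by 16 onset days per completer for non-serious events (17 if the SAP formula is set against a plain 30-day offset). On the literal reading, the percentage also depends on whether the subject completed.

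The practical effect should be small. The endpoint is descriptive and the bioequivalence analysis is unaffected. Each regimen is last in exactly one sequence (D, A, B, C for Sequences I to IV), so among completers the cut falls evenly over regimens. Between 11 and 17 of the uncounted days rely on spontaneous reports. These counts assume doses exactly 7 days apart and study exit on Day 4 of Period 4.

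**What to change.** Amend SAP 7.11.1 as follows:

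1. Use one window for all AEs, serious or not, and for all subjects. Either adopt Protocol 13.1.4 (onset date − last-dose date ≤ 30), or choose another window, declare it as a departure from 13.1.4, and apply it identically to completers and non-completers.
2. Make the formula give the same last day as the prose, and say whether the dosing day counts as Day 1.
3. Attribute every TEAE after a subject's final dose, including SAEs, to the last regimen received, and delete the separate non-completer window.
4. Start the late-AE listing where the TEAE window ends, so that no event falls between them.

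The cost is SAP wording, one date cut-off in the AE program and the start day of one listing. No new data are needed.

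As a separate text correction, reconcile the anchor of the follow-up call (last dose or study exit) across Protocol 6.1, 9.3.5, 10.2.1.1 and Appendix A.

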7.11.2 Clinical Laboratory Evaluations

Laboratory samples will be obtained following a minimum 8-hour overnight fast on Day 1 of Period 1 (pre-dose), and Day 4 of Period 4 (or Study Exit in case of early termination), see Appendix A. Baseline will be defined as the Day 1 value.

Laboratory values for hematology, serum chemistry, and urinalysis, see protocol section 9.1.8, will be summarized by regimen and by all subjects Overall. Individual subject values together with treatment sequence assignment will be presented in data listing; values that meet the Takeda predefined markedly abnormal value (MAV) criteria, [Appendix B](#), and/or outside normal range will be flagged in the data listing. For each laboratory parameter, where possible, the following will be performed:

- Descriptive statistics for change from baseline,

- Number and percentage of subjects with a value outside normal range,
- Number and percentage of subjects with a value meeting MAV criteria.

Individual results for hematology and chemistry laboratory tests that meet the Takeda predefined laboratory markedly abnormal value (MAV) criteria in [Appendix B](#) will be presented in a data listing. If a subject has an MAV for a laboratory test, all visits for that subject for that parameter will be listed.

All clinical laboratory data will be presented in both SI and conventional units in the data listings. Laboratory data outside of the normal reference range will be listed. Out of normal range values and MAVs will be flagged in data listings.

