If subjects experience ALT or AST >3 ×upper limit of normal (ULN), follow-up laboratory tests (at a minimum, serum alkaline phosphatase, ALT, AST, total bilirubin, GGT, and international normalized ratio [INR]) should be performed within a maximum of 7 days and preferably within 48 to 72 hours after the abnormality was noted. (Refer to Section 10.2.3 for the appropriate guidance on reporting abnormal liver function tests.)

If the ALT or AST remains elevated >3 ×ULN on these 2 consecutive occasions, the investigator must contact the Medical Monitor for consideration of additional testing, close monitoring, possible discontinuation of study drug, discussion of the relevant subject details and possible

alternative etiologies. The abnormality should be recorded as an AE (please refer to Section 10.2.3 for reporting requirements).

The investigator will maintain a copy of the laboratory accreditation and the reference ranges for the laboratory used.

Laboratory reports must be signed and dated by the investigator indicating that the report has been reviewed and any abnormalities have been assessed for clinical significance.

All laboratory abnormalities must be recorded as an AE in the subject's source documents and on the appropriate eCRF. A clinically significant laboratory abnormality that has been verified by retesting will be followed until the abnormality returns to an acceptable level or a satisfactory explanation has been obtained.

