10.1.3 Additional Points to Consider for AEs

An untoward finding generally may:

- Indicate a new diagnosis.
- Necessitate therapeutic intervention.
- Require an invasive diagnostic procedure.
- Require discontinuation or a change in dose of study drug or a concomitant medication.
- Be considered unfavorable by the investigator for any reason.

AEs caused by a study procedure (eg, a bruise after blood draw) should be recorded as an AE.

Diagnoses vs signs and symptoms:

- Each event should be recorded to represent a single diagnosis. Accompanying signs (including abnormal laboratory values or ECG findings) or symptoms should NOT be recorded as additional AEs. If a diagnosis is unknown, sign(s) or symptom(s) should be recorded appropriately as an AE(s).

Laboratory values and ECG findings:

- Changes in laboratory values or ECG findings are considered to be AEs. Repeated or additional noninvasive testing for verification, evaluation or monitoring of an abnormality is allowed.
- If abnormal laboratory values or ECG findings are the result of pathology for which there is an overall diagnosis (eg, increased creatinine in renal failure), the diagnosis only should be reported appropriately as an AE.

Pre-existing conditions:

- Subjects with pre-existing medical conditions will not be enrolled to this study.

Worsening of AEs:

- If the subject experiences a worsening or complication of an AE, the worsening or complication should be recorded as a new AE. Investigators should ensure that the AE term recorded captures the change in the condition (eg, “worsening of...”).

Changes in intensity of AEs:

- If the subject experiences changes in intensity of an AE, the event should be captured once with the maximum intensity recorded.

Elective surgeries or procedures:

- Elective surgeries or procedures are not permitted during the trial; should they be required, the subject will be withdrawn.

Overdose:

- Cases of overdose with any medication without manifested side effects are NOT considered AEs, but instead will be documented on an Overdose page of the eCRF. Any manifested side effects will be considered AEs and will be recorded on the AE page of the eCRF.

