7.1.3 Definition of Study Visit Windows

All blood samples should be identifiable by date and time. If actual time is missing then the nominal time may be used in the analyses. Safety laboratory collections (i.e. clinical laboratory evaluations) are obtained Pre-dose on Day 1 (baseline) and Day 4 of Period 4 (post-baseline). If a subject has more than one laboratory value (eg. a repeat laboratory draw) then the latter will be used for data analyses.

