- (f) ECG performed at Screening, Check-in (Day -1 of Period 1), and Study Exit Day 4 of Period 4, or if a subject terminates early from the study.
- (g) Hematology, serum chemistries, and urinalysis tests will be done at a local laboratory.
- (h) Predose hematology, serum chemistries, and urinalysis tests will be done for Period 1 only.
- (i) A urine pregnancy test and HBsAg, Anti-HCV, HIV, and syphilis tests will be done locally.
- (j) Following the 24-hour blood sample collection on Day 2 of each period, subjects will be discharged from the clinic and will return to the clinic for the 36-hour blood sample collection on Day 2 and on Days 3 and 4 of each period to complete study procedures.
- (k) Study drug will be administered on Day 1 of each period at 08:00 (± 1) hours, following an 8- hour fast. Dosing may be staggered to help facilitate logistics at the site.
- (l) Blood samples for PK obtained predose (within 15 minutes prior to dose), 0.25, 0.5, 1, 1.5, 2, 3, 4, 6, 8, 12, 16, 24, 36, 48, and 72 hours postdose. The PK sample should not be collected at the Early Termination Visit if a PK collection is not scheduled.
- (m) Predose AEs will be captured immediately following the signing of the informed consent at Screening until dosing on Day 1 of Period 1. The routine collection of AEs will continue through to the follow-up phone call.

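### By-regimen laboratory summaries (SAP 7.11.2, Protocol 13.1.4) cannot compare test with reference, because a completer's only scheduled post-dose sample follows all four regimens

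*SAP*

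**What the plan says.** On grouping, SAP 7.11.2 states: "Laboratory values for hematology, serum chemistry, and urinalysis, see protocol section 9.1.8, will be summarized by regimen and by all subjects Overall". For each parameter it lists change from baseline, the number outside the normal range, and the number meeting the markedly abnormal criteria. Protocol 13.1.4 asks for observed laboratory values and changes from baseline by regimen, and for observed ECG values by regimen.

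On timing, SAP 7.1.3 states: "Safety laboratory collections (i.e. clinical laboratory evaluations) are obtained Pre-dose on Day 1 (baseline) and Day 4 of Period 4 (post-baseline". SAP 7.11.2 gives the post-dose sample as "Day 4 of Period 4 (or Study Exit in case of early termination", and Appendix A footnote (h) adds: "Predose hematology, serum chemistries, and urinalysis tests will be done for Period 1 only". ECGs follow the same pattern: Screening, Day -1 of Period 1, and study exit (Appendix A, footnote (f)).

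On attribution, SAP 7.11.1 assigns adverse events to regimens. An event after the last-period dose and within 14 days of it "is attributed to the regimen received in the last period". SAP 7.1.4 and 7.1.5 deal with missing dates for events and concomitant medication. For laboratory values the only selection rule is in SAP 7.1.3: the later of repeated values is used.

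For ECGs, SAP 7.11.4 plans a shift table without naming its grouping. The parent section, SAP 7.11, sets a default of study arm for all safety summaries.

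**The concern.** A by-regimen table in a crossover is normally read as a within-subject comparison, with each subject contributing a value under each regimen. Vital signs can support such a table because they are scheduled on Day 4 of every period. Laboratory tests and ECGs are not, so their columns would carry test and reference labels without holding test and reference data. A programmer would also have to choose an attribution rule unaided, and the two obvious choices give very different tables. At stake is whether descriptive safety tables in a registration study are read correctly.

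**Working it through.** **1. Samples per subject.** Protocol Table 9.c lists clinical laboratory samples as 1 at Screening and then 1, 0, 0 and 1 in Periods 1 to 4. At 13 mL for Screening and 10 mL otherwise, 13 + 10 + 10 = 33 mL, which reproduces the table's total. A completer therefore has one scheduled post-dose value. One value per regimen per subject would need 4 × 72 = 288; at most 72 are scheduled.

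**2. Timing.** With doses 7 days apart and the exit sample 3 days after the fourth dose, the sample falls at least 3 × 7 + 3 = 24 days after the first dose, 17 after the second, 10 after the third and 3 after the fourth.

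**3. Last-regimen rule.** From the design figure:

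| Sequence | Order | Last regimen |
|---|---|---|
| I | A, B, C, D | D |
| II | B, C, D, A | A |
| III | C, D, A, B | B |
| IV | D, A, B, C | C |

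Among completers, A versus B becomes Sequence II versus Sequence III, and C versus D becomes Sequence IV versus Sequence I. These are different people, each exposed to all four regimens, and the columns also differ in which regimen came just before the last one (D before A, A before B, B before C, C before D). At most this is a between-subject contrast, valid only if the effects of earlier doses do not differ by regimen and order.

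**4. Every-regimen-received rule.** Each completer's single value enters all four columns, so the columns are identical for completers and every difference between them is zero by construction.

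**5. Precision under the last-regimen rule.** At the planned 14% dropout, 0.14 × 72 = 10.1, leaving about 62 completers, or 15.5 per sequence. Early-exit subjects can also supply a value, so a column holds about 15 to 18. The standard error of a mean change, in SD units, is 1/√n: 0.236 for n = 18 and 0.258 for n = 15, against 0.118 for n = 72 and 0.127 for n = 62 overall. These figures describe precision only; they do not measure misattribution.

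**6. The link to adverse events.** Protocol 9.1.8 says "All laboratory abnormalities must be recorded as an AE" and Protocol 10.1.3 says "Changes in laboratory values or ECG findings are considered to be AEs". A new abnormality with onset dated at the exit visit gives 3 + 1 = 4, within the 14-day limit, so it counts under the last regimen. The share that truly began there cannot be known from the documents. Assume that abnormalities start equally often in each period and persist into the next with probability q. The share is then 1/(1 + q + q² + q³):

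| q (assumed) | 0 | 0.25 | 0.5 | 0.75 | 1 |
|---|---|---|---|---|---|
| Share from last regimen | 100% | 75% | 53% | 37% | 25% |

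**The case against.** The strongest reply is that little depends on these columns. The comparative objective covers adverse-event data only. The laboratory and ECG endpoints ask whether a subject ever had a clinically significant change after dosing, which an overall summary answers. That summary and listings showing treatment sequence are already planned. All of this stands and keeps the point minor. The qualifiers where possible (SAP 7.11.2) and where appropriate (Protocol 13.1.4) do not settle it, because they assign no value to a regimen.

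A reader might infer that the by-regimen adverse-event tables are wrong too. The documents do not support that. SAP 7.11.1 has an explicit, prespecified rule, and Protocol 6.2 gives a 7-day washout of more than five half-lives for both drugs. Washout does not exclude a persisting abnormality, but how often an exit finding is mislabelled depends wholly on the assumed persistence shown above. Events must have started or worsened after the first dose, and where a diagnosis explains a finding, Protocol 10.1.3 records only the diagnosis. With balanced sequences the rule has no evident tilt towards test or reference.

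A reader might also infer that the ECG shift table has no grouping at all. It has the SAP 7.11 default; the difficulty is that study arm has no defined meaning where every subject is planned to receive all four regimens.

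**Conclusion.** The concern holds for the laboratory summary in SAP 7.11.2 and Protocol 13.1.4, and for the by-regimen ECG summary in Protocol 13.1.4. Under either natural rule the completers' columns are sequence groups or copies of one another. This follows from the schedule and the design figure and needs no assumption about drug effects. It is stated for completers: a subject who stops after Period 1 has a value belonging to one regimen, and unscheduled repeat tests may add values without giving one per regimen.

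Severity is minor. The tables are descriptive, and neither the bioequivalence analysis nor the sample size is touched. For adverse events, the documents support no more than a note that attributing exit findings to the last regimen is a convention.

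**What to change.** - **SAP 7.11.2:** drop the by-regimen laboratory columns and keep the overall summary, optionally also by sequence. Label it as end-of-study change after all doses received, and identify early-exit values by number of doses taken.
- **SAP 7.11 and 7.11.4:** state that the ECG shift table is overall, optionally by sequence, so that the study-arm default does not govern it.
- **SAP 7.13:** record the departure from Protocol 13.1.4, or align the protocol text at its next amendment.
- **Optional, SAP 7.11.1:** add a general footnote to the by-regimen adverse-event tables saying that new laboratory or ECG abnormalities first detected at the exit visit are assigned to the last regimen by convention and may have arisen earlier. No event-level flag is needed; one would require a rule linking events to how they were detected, which the plan does not have.

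The cost is a SAP revision with re-approval. There are no new samples or visits, and no protocol amendment is needed for this point alone; a later alignment of Protocol 13.1.4 would need ethics approval with that amendment. The downside is the loss of the by-regimen laboratory and ECG columns.
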